6.1.2.2 Day 15 (± 3 days) (Visit 2)

Patients will arrive at the study centre in the morning of day 15 after having taken study treatment at home in the morning. The following procedures will be performed:

- A 12-lead ECG in a supine position after at least 10 minutes rest. An ECG with a QTcF > 500 ms should be confirmed by a second ECG taken 1-2 hours later.
- BP and HR (unless recorded by ECG) in a supine position after at least 10 minutes rest
- Laboratory safety assessments (haematology, chemistry and urinalysis)
- Date of first SSE

- Date of first prostate cancer-related invasive procedure
- Status of survival
- Current medical condition, AEs and concomitant treatments

Patients will continue taking study treatment at home until day 29 visit (visit 3).

6.1.2.3 Day 29 (\pm 5 days) (Visit 3)

The patient will arrive at the study centre in the morning of day 29 after having taken study treatment at home in the morning. The following procedures will be performed:

- Physical examination including weight
- A 12-lead ECG in a supine position after at least 10 minutes rest. An ECG with a QTcF > 500 ms should be confirmed by a second ECG taken 1-2 hours later.
- BP and HR (unless recorded by ECG) in a supine position after at least 10 minutes rest
- Laboratory safety assessments (haematology, chemistry and urinalysis)
- Date of first SSE
- Date of first prostate cancer-related invasive procedure
- Status of survival
- Current medical condition, AEs and concomitant treatments
- Study drug will be dispensed for 12 weeks and accountability performed
- Dispensing pain diary

Patients will continue taking study drug at home until week 16 visit (visit 4).

6.1.2.4 Week 16 (\pm 7 days) (Visit 4) and every subsequent 16 weeks (\pm 7 days) thereafter

The patient will arrive at the study centre in the morning of week 16 (and every subsequent 16 weeks) after having taken study treatment at home in the morning. The following procedures will be performed:

- BPI-SF and EORTC-QLQ-PR25 questionnaires at each visit
- EQ-5D-3L and FACT-P at week 16 only, and PCS subscale of FACT-P every 16 weeks thereafter
- Physical examination including weight
- A 12-lead ECG in a supine position after at least 10 minutes rest. An ECG with a QTcF > 500 ms should be confirmed by a second ECG taken 1-2 hours later
- BP and HR (unless recorded by ECG) in a supine position after at least 10 minutes rest
- ECOG performance status
- Laboratory safety assessments (haematology, chemistry and urinalysis), and testosterone and PSA
- Chest, abdomen and pelvic CT/MRI **and** bone scan

Local review should always be completed as soon as possible. All scans should then be submitted for independent blinded central reading during the double-blind treatment phase, on an ongoing basis, according to the timelines described in the imaging manual. All patient scans will undergo central imaging review during the double-blind treatment phase. If the local qualified physician (e.g. site radiologist or PI, at the PI's discretion) suspects the presence of metastasis, this should be recorded in the CRF. The presence or absence of metastasis will need to be confirmed by independent blinded central reading. Patients should remain on treatment until deemed metastatic by central review.

- Date of first SSE
- Date of first prostate cancer-related invasive procedure
- Status of survival
- Current medical condition, AEs and concomitant treatments.
- Study drug will be dispensed for 16 weeks and accountability performed
- Collection of pain diary and dispensing a new pain diary

Patients will continue taking study drug at home until next visit.

6.1.2.5 Start of open-label treatment visit

Under the conditions outlined in Section 5.9, patients who choose to receive open-label darolutamide will have a start of open-label treatment visit at the time point of study treatment

code unblinding. Those patients who do not choose to continue with open-label darolutamide treatment, will have an end-of-study treatment visit at this point of time (see Section 6.1.2.6).

The following procedures will be performed during the start of open-label treatment visit:

- QoL:
 - BPI-SF and EORTC-QLQ-PR25: all patients
 - FACT-P and EQ-5D-3L: placebo patients crossing over to open-label darolutamide treatment
 - PCS-subscale of FACT-P: patients in the darolutamide arm continuing open-label darolutamide treatment

If the end of the double-blind treatment period occurs less than 16 weeks from the start of study treatment, the EQ-5D-3L assessment is required in the first 16 weeks of open-label darolutamide treatment.

- Physical examination including weight
- A 12-lead ECG in a supine position after at least 10 minutes rest. An ECG with a QTcF > 500 ms should be confirmed by a second ECG taken 1-2 hours later. 12-lead ECG will be performed only at the start of open-label visit. ECG is not required on subsequent visits during the open-label darolutamide treatment.
- BP and HR (unless recorded by ECG) in a supine position after at least 10 minutes rest
- Laboratory safety assessments (haematology, chemistry and urinalysis) and PSA
- Chest, abdomen and pelvic CT/MRI **and** bone scan. Scans are acceptable if performed within 42 days prior to the start of open-label treatment visit. Imaging will be conducted every 16 weeks (± 7 days) during the open-label darolutamide treatment after the start of open-label treatment visit. Central confirmation of local imaging is not required during the open-label darolutamide treatment.
- A blood (plasma) sample for tumour-related biomarker analysis unless precluded by local guidelines, e.g. IEC/IRB or regulatory authorities (see Section 6.5)
- ECOG performance status
- Date of first SSE
- Date of first prostate cancer-related invasive procedure
- Status of survival
- Current medical condition, AEs and concomitant treatments
- Collection of pain diary and dispensing a new pain diary

- Return of all remaining study drugs and study drug containers and drug accountability performed. Study drug for the open-label treatment phase will be dispensed for 16 weeks.

Patients in the darolutamide arm continuing open-label darolutamide treatment will have subsequent visits every 16 weeks according to [Table 3](#) until metastasis is seen by local reading. After occurrence of metastasis, the patients should discontinue study treatment and will be followed thereafter every 16 weeks for secondary and additional variables (see [Table 4](#)).

Patients in the placebo arm crossing over to open-label darolutamide treatment will have subsequent visits every 16 weeks according to [Table 4](#) until metastasis is seen by local reading. After occurrence of metastasis, the patients should discontinue study treatment and will be followed every 16 weeks for secondary and additional variables (see [Table 4](#)).

6.1.2.6 End-of-study treatment visit, and in transition to the roll-over study

Patients will have an end-of-study treatment visit 28 days (+7 days) after the last dose of study treatment or before transition to the roll-over study. Another systemic antineoplastic therapy may be initiated no sooner than 7 days after the last dose of study treatment.

Note: the end-of-study treatment visit procedures for placebo patients crossing over to open-label darolutamide treatment are described in [Table 4](#) instead.

The following procedures will be performed during the end-of-study treatment visit:

- BPI-SF, FACT-P, EORTC-QLQ-PR25 and EQ-5D-3L questionnaires
- Physical examination including weight
- Only for the double-blind treatment period: A 12-lead ECG in a supine position after at least 10 minutes rest. An ECG with a QTcF > 500 ms should be confirmed by a second ECG taken 1-2 hours later
- BP and HR (unless recorded by ECG) in a supine position after at least 10 minutes rest
- Laboratory safety assessments (haematology, chemistry and urinalysis) and PSA
- A blood (plasma) sample for tumour-related biomarker analysis unless precluded by local guidelines, e.g. IEC/IRB or regulatory authorities (see [Section 6.5](#))
- ECOG performance status
- Date of first SSE
- Date of first prostate cancer-related invasive procedure
- Status of survival
- Current medical condition, AEs and concomitant treatments
- Collection of pain diary and dispensing a new pain diary. No pain diary will be dispensed when a patient is transitioning to the roll-over study.

- Return of all remaining study drugs and study drug containers and drug accountability performed

6.1.3 Follow-up period

Patients with MFS events (double-blind treatment phase) or metastasis by local reading (open-label treatment phase) will enter the follow-up period and will be contacted every 16 weeks until death or the end of the study. Follow-up contact will be performed by visit or telephone. The following data will be captured during the follow-up contacts:

- BPI-SF and PCS subscale of FACT-P questionnaires. If the patient is contacted through physician visit, a paper questionnaire will be completed by the patient prior to meeting with the physician in the office. If the patient is contacted by phone, the caller will read each item from the questionnaires to the patient and record the responses on a paper questionnaire.
- ECOG performance status
- Any AEs or SAEs that occur after the end-of-study treatment visit and which are considered to be related to the study treatment or any study procedures have to be reported and entered into the CRF.
- Collection of concomitant treatments used to treat new related or unresolved related AEs, if applicable)
- Status of survival
- Date of first SSE
- Date of first prostate cancer-related invasive procedure
- Use of systemic antineoplastic therapies
- Collection of pain diary and dispensing a new pain diary, and collection of pain medications. If the patient is contacted by phone, the pain diary will be mailed back to the clinic. No pain diary will be dispensed when a patient is transitioning to the roll-over study.

In case the patient discontinues study treatment before confirmed metastasis in the double-blind treatment phase or metastasis by local reading in the open-label treatment phase without initiating any prohibited treatment, these patients will be followed as outlined in [Table 4](#) until the end of the study.

The follow-up period will end at each site when all patients at the site who are ongoing on treatment have transitioned into the roll-over study or discontinued from the study for another reason (e.g., consent withdrawn - with no further data collection, lost to follow-up). Patients who are in follow-up at the site will end follow-up.

6.1.4 Unscheduled visits

In the event that there are significant abnormal safety findings or suspected disease progression, control assessments may be performed at any time during the study treatment period according to the judgment of the investigator. The following procedures (one or more) may be performed at the unscheduled visit, if indicated:

- Physical examination including weight
- 12-lead ECG
- BP and HR
- Laboratory safety assessments (haematology, chemistry, urinalysis)
- Status of survival
- AEs, current medical condition, concomitant treatments
- Chest, abdomen and pelvic CT/MRI or x-ray
- Bone scan

Survival data will be collected through an additional survival sweep. All patients considered alive shortly after the database cut-off date for the MFS analysis and prior to any subsequent analysis of OS will be contacted for survival status.

6.1.5 Roll-over study

A separate roll-over study (study 20321) has been set up to allow patients who received darolutamide in the course of Bayer-sponsored clinical trials to continue receiving treatment with darolutamide at the time of study discontinuation.

The roll-over study is subject to approval by the competent health authority and ethics committee. The roll-over study protocol will be available to patients as long as darolutamide is not approved and reimbursed in a specific country.

All study patients who are ongoing on treatment and eligible to enter the roll-over study will transition as soon as it has been approved by local ethics committee/independent review board/health authority and the site is ready to receive patients. Patients who will transition to the roll-over study will perform the end-of-study treatment visit in the current study as outlined in [Table 3](#) and [Table 4](#), after which they may be transitioned. When the last patient at a given site has transitioned into the roll-over study, all other patients in follow-up at that site will perform the end-of-study visit.

All patients who transition into this separate study will require a separate signed informed consent.

If approval and reimbursement of darolutamide becomes available after a patient has been enrolled in the roll-over study, patients have 2 months to be transitioned to commercial supplies.

6.1.6 End of study

For each participating EU country, the end of the study according to the EU Clinical Trial Directive will be reached when the last patient last visit date has been reached in the respective country. This study will end when all patients on treatment have transitioned into the roll-over study or have discontinued from this study for another reason (e.g., death, consent withdrawn - with no further data collection, lost to follow-up). Until the transition to the roll-over study, patients will continue to follow all the protocol required procedures and visits in the current protocol.

At each site, when all patients on treatment are moved to a roll-over study or have discontinued, all ongoing patients (i.e. in follow-up) will be discontinued, as the current study will be terminated.

Once the roll-over study 20321 is available for patients to move to, study treatment in the current study will no longer be available.

6.2 PK assessments during double-blind treatment

No samples for PK will be collected during the open-label treatment period.

The following PK-related procedures will be performed at study centres participating in PK sample collection, to ensure evaluable samples are collected in approximately 600 patients:

- In total, four sparse PK samples (one trough, two early and one late sample) will be collected at different visits (see [Figure 1](#) for details). The samples will be collected within 3 sampling windows:
- Trough: at least 10 hours after the evening dose on the preceding day and before morning dosing on the day of PK sampling
- Early: between 1 and 6 hours after the morning dose on the day of PK sampling
- Late: between 4 and 12 hours after the morning dose and before the next dosing on the day of PK sampling.

Samples taken on the same occasion will be separated by at least 2 hours. If PK sampling is not feasible during the proposed visits, later visits may be used to obtain PK samples.

Sampling times outside the suggested time windows will not be considered as protocol deviations. It is of importance that the actual date and time of blood sampling are documented in the eCRF because PK calculations will be based on the actual sampling times relative to dosing times.

An example order of sampling is given below:

- Visit 2 – Trough sample + Early sample
- Visit 3 – Early sample
- Visit 4 – Late sample

On occasions when trough and early PK samples are to be collected at the same day, patients will be instructed to take their morning dose of study treatment at the study site after the trough PK sample has been collected. Dosing will be witnessed by the study personnel.

[figure not shown]
On the occasion when only early or late PK samples are to be collected, the patient will be instructed to take study treatment at home in the morning. Exact date and time of dosing and each PK sample collection will be recorded. Patient will use the PK diary to record the required date and time of home dosing.

Additional PK samples may be collected in the event of early study treatment discontinuation. When additional PK samples are collected, the dates and times of sample collection and the 2 doses of study treatment preceding sample collection will be recorded.

The following 12-lead ECG and vital sign measurements will be performed before each PK sampling:

- A triplicate 12-lead ECG including HR in a supine position after at least 10 minutes rest. The 3 consecutive recordings will be performed within approximately 5 minutes.
- BP and HR (unless recorded by ECG) in a supine position after at least 10 minutes rest.

Figure 1. Overview of study treatment dosing and PK blood sampling

¹ Record the date and time for the 2 doses of study treatment on the day prior to PK sampling. On the day of PK sampling record the time for the morning dosing at the study centre or at home, as applicable.

² Before each PK sampling, triplicate 12-lead ECG including HR and a single BP will be recorded in a supine position after at least 10 minutes rest. The 3 consecutive (triplicate) recordings will be performed within approximately 5 minutes.

6.3 Assessment of efficacy variables

6.3.1 Primary efficacy variable

The primary efficacy variable is MFS, defined as time between randomisation and evidence of metastasis or death from any cause, whichever occurs first.

Chest, abdomen, and pelvic CT/MRI and nuclear medicine bone scan will be performed at screening (baseline) and every 16 weeks until confirmed metastasis. Absence or presence of metastasis will be confirmed by the independent blinded central reading during the double-blind treatment phase.

Conventional CT and MRI should be used with cuts of 10 mm or less in slice thickness contiguously. Spiral CT should be performed using ≤ 5 mm contiguous reconstruction, and both reconstructions should be done using both a bone (edge-enhancing) and a soft tissue algorithm.

Metastasis in bone is defined as appearance of 1 or more lesions that are confirmed by the central reading according to the one of the methods described below. If the central reading identifies changes on bone scan, confirmatory anatomic imaging CT/MRI or x-ray, of the area in question needs to be obtained. Anatomic imaging performed up to 2 weeks prior to bone scan or later may be used as a confirmatory scan. Appearance of bone metastasis is assigned to the date of the bone scan at which the lesion was first identified.

Metastasis in non-osseous tissue is defined as new distant pathologic lymph nodes (M1a) or other pathological lesion (M1c) according to RECIST 1.1. New or progressive regional pathologic lymph nodes will not be defined as metastasis.

Upon central confirmation of metastasis (local reading during open-label darolutamide treatment), the patient must be withdrawn from study treatment. If the reading does not confirm metastasis, the patient will continue study treatment as specified in [Table 3](#). Patients with new or progressive regional pathologic lymph nodes will continue study treatment.

Status of metastasis will be assessed from randomisation until first metastasis throughout the study treatment period.

Patients withdrawing from study treatment before metastasis during the double-blind treatment but not initiating any subsequent prohibited antineoplastic therapy will be followed as outlined in [Table 4](#).

Instructions on image acquisition and submission of scans for central reading will be provided in the imaging manual.

6.3.2 Secondary efficacy variables

6.3.2.1 Overall survival

OS is defined as time from randomisation to date of death from any cause. Date of death and primary cause of death will be recorded.

Survival status will be assessed from randomisation until the end of follow-up period.

6.3.2.2 Time to first symptomatic skeletal event (SSE)

Time to first SSE is defined as time from randomisation to the first occurrence of SSE. Date of the first SSE will be recorded.

SSE is defined as EBRT to relieve skeletal symptoms, new symptomatic pathologic bone fracture, or occurrence of spinal cord compression or tumour-related orthopaedic surgical intervention, whichever comes first.

SSE will be assessed from randomisation until the first occurrence of SSE.

6.3.2.3 Time to initiation of first cytotoxic chemotherapy

Time to cytotoxic chemotherapy is defined as time from randomisation to initiation of the first cytotoxic chemotherapy. Name and start date of cytotoxic chemotherapy treatment will be recorded.

Use of cytotoxic chemotherapy will be assessed from randomisation until the first use of cytotoxic chemotherapy.

6.3.2.4 Time to pain progression

Pain progression is defined as an increase of ≥ 2 points from baseline (day 1 score) in question 3 of BPI-SF (related to the worst pain in the last 24 hours) taken as a 7-day average, or initiation of short or long-acting opioids for pain, whichever comes first.

Pain will be assessed with the BPI-SF questionnaire (Appendix 4) during the visit, pain diary entries from 6 days preceding the visit and opioid use from baseline until documented pain progression. The pain diary consists of 6 copies of BPI-SF questionnaire.

Initiation or change in the use of other non-opioid analgesics is not used in the analysis of pain progression.

6.3.3 Additional efficacy variables

6.3.3.1 Progression-free survival

PFS is defined as time between randomisation and evidence of any radiographic disease progression, including new pathologic lymph nodes identified above or below the aortic bifurcation or death from any cause, whichever occurs first.

Status of PFS will be assessed from randomisation until the first evidence of radiographic disease progression.

6.3.3.2 Time to first prostate cancer-related invasive procedure

Time to first prostate cancer-related invasive procedure is defined as time from randomisation to date of first prostate cancer-related invasive procedure.

Prostate cancer-related invasive procedure is defined as any procedure needed for alleviation of symptoms, signs or findings caused by progression of prostate cancer (e.g. catheterisation of the bladder, percutaneous drainage of hydronephrosis, palliative electroresection of the prostate, etc.).

Status of prostate cancer-related invasive procedures will be assessed from randomisation until the first prostate cancer-related invasive procedure.

6.3.3.3 Time to initiation of subsequent antineoplastic therapy

Time to initiation of subsequent antineoplastic therapy is defined as time from randomisation to initiation of first antineoplastic therapy.

Subsequent antineoplastic therapy will be assessed from the first follow-up visit until the first use of such therapy.

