 - ¹³ Blood (plasma) sampling for tumour-related biomarker evaluation will be collected on day 1 visit before study treatment administration, at the start of open-label treatment visit, and at the end-of-study treatment visit unless precluded by local guidelines, e.g. IEC/IRB or regulatory authorities. For placebo patients crossing over to open-label darolutamide treatment, sampling will not be performed at the end-of-study treatment visit (see [Table 4](#)).
 - ¹⁴ The local PSA result taken at screening should be used to confirm the patient has CRPC (inclusion criterion 4) and meets inclusion criterion 6.
 - ¹⁵ Only study drug accountability performed at the end-of-study treatment visit.
 - ¹⁶ A blood sample for DNA extraction will be taken at day 1 visit (or later during the study if feasible) only from patients who have signed the PG IC unless precluded by local guidelines, e.g. IEC/IRB or regulatory authorities.
 - ¹⁷ 12-lead ECG will be performed only at the start of open-label visit. ECG is not required on subsequent visits during the open-label darolutamide treatment.
 - ¹⁸ Survival data will also be collected through an additional survival sweep. All patients considered alive shortly after the database cut-off date for the MFS analysis and prior to any subsequent analysis of OS will be contacted for survival status.

Table 4. Study event schedule after withdrawal of study treatment or during the follow-up period; and study event schedule for placebo patients crossing over to open-label darolutamide treatment

Protocol activities	For patients discontinuing study drug before confirmed metastasis and not initiating any prohibited treatment *	For patients after confirmed metastasis, or receiving subsequent treatment after unblinding *	For placebo patients crossing over to open-label darolutamide	
	Visits Every 16 weeks (±7 days) from end-of-study treatment visit ¹	Visits or phone contacts Every 16 weeks (±7 days) from end-of- study treatment visit ²	Visits Every 16 weeks (±7 days) from start of open-label treatment visit ¹	End-of-study treatment visit 28 days (+7 days) after last dose or in transition to roll-over study
BPI-SF	X	X	X	X
Dispensing of pain diary	X	X	X	X
Collection of pain diary and pain medications	X ³	X ³	X ³	X
PCS subscale of FACT-P	X	X	X	X
ECOG performance status	X	X	X	X
Use of subsequent antineoplastic therapies	X	X	X	X
Laboratory safety assessments			X	X

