Collection of AEs and SAEs considered to be related to study treatment or procedures	X	X	X ⁵	X ⁵
Collection of concomitant treatments used to treat new related or unresolved related AEs	X	X	X	X
Darolutamide dispensing and accountability			X	X ⁷
First SSE	X	X	X	X
First prostate cancer-related invasive procedure for prostate cancer	X	X	X	X
Survival status ⁸	X	X	X	X
Serum PSA	X		X ⁶	
Chest, abdomen, and pelvic CT/MRI	X		X ⁶	
Bone scan ⁴	X		X ⁶	

Abbreviations: ECOG = Eastern Cooperative Oncology Group; EOS = end-of-study; PSA = prostate-specific antigen; SSE = symptomatic skeletal event

* Note: In case a patient initiates a prohibited treatment during the open-label treatment phase before metastasis confirmed by local reading, the patient must discontinue study treatment and will be followed for survival until the end of the study (see Section 4.7.1 for additional details).

¹ Until metastasis, death, transition to a roll-over study, or the end of the study

² Until death or the end of the study

³ Patients will be instructed to complete the diary for 6 days before each 16-week visit until documented pain progression. Pain medications will be recorded on CRFs at each 16-week visit until documented pain progression.

⁴ New lesion(s) in bone scan must be confirmed by CT/MRI (whichever imaging was conducted at screening for soft tissue) or x-ray. If confirmatory scan is negative (does not confirm progression), the patient will continue to visit study centre as specified in the study event table.

- ⁵ For placebo patients crossing over to open-label darolutamide, all AEs and SAEs irrespective of relatedness will be captured.
- ⁶ Placebo patients crossing over to open-label darolutamide will have central PSA testing and local imaging, radiology .
- ⁷ Only drug accountability performed at the end-of-study treatment visit.
- ⁸ Survival data will also be collected through an additional survival sweep. All patients considered alive shortly after the database cut-off date for the MFS analysis and prior to any subsequent analysis of OS will be contacted for survival status.

Patients initiating a prohibited treatment before confirmed metastasis will be followed only for survival status every 16 weeks until the end of the study.

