**Table 11: Censoring Rules for Cytotoxic Chemotherapy**

Situation	End Date on or prior to cut-off date	Censored
Recorded cytotoxic chemotherapy during the study	Date of the first assessment that qualified as cytotoxic chemotherapy	No
Death during the study before cytotoxic chemotherapy	Date of last visit at which cytotoxic chemotherapy question was collected or randomization date whatever comes later	Yes
Patient has no recorded cytotoxic chemotherapy at data cut-off	Date of last visit at which cytotoxic chemotherapy question was collected or randomization date whatever comes later	Yes

Patient lost to follow-up before data cut-off	Date of last visit at which cytotoxic chemotherapy question was collected or randomization date whatever comes later	Yes
---	--	-----

Cytotoxic chemotherapy is a specific antineoplastic therapy and therefore the CRF question “Has the patient taken any new antineoplastic therapy since previous visit?” implies the question for cytotoxic chemotherapy.

This endpoint is selected from the ADTTE dataset using variable PARAMCD equal to ‘CYTOC’.

A log rank test stratified by stratification factor of PSADT ( $\leq 6$  vs.  $> 6$  months) and use of osteoclast-targeted therapy (yes vs. no) at randomization will be used to compare the darolutamide treated and placebo groups.

The hazard ratio as well as its 95% CI will be presented based on fitting a Cox regression model with treatment as factor and stratified by PSADT ( $\leq 6$  vs.  $> 6$  months) and use of osteoclast-targeted therapy (yes vs. no) at randomization.

Kaplan-Meier survival curves (product-limit estimates) will be presented by treatment arm. The Kaplan-Meier estimate of the median survival time and first and third quartiles will be presented with 95% CI. Greenwood's formula will be used for the standard error of the Kaplan-Meier estimate in the calculation of these confidence limits.

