**Table 16: Censoring Rules for antineoplastic therapy**

Situation	End Date on or prior to cut-off date	Censored
Recorded antineoplastic therapy during the study	Date of the first assessment that qualified as antineoplastic therapy	No
Death during the study before antineoplastic therapy	Date of last visit at which antineoplastic therapy question was collected or randomization date whatever comes later	Yes
Patient has no recorded antineoplastic therapy at data cut-off	Date of last visit at which antineoplastic therapy question was collected or randomization date whatever comes later	Yes
Patient lost to follow-up before data cut-off	Date of last visit at which antineoplastic therapy question was collected or at the data cut-off, whichever occurs first	Yes

This endpoint is selected from the ADTTE dataset using variable PARAMCD equal to 'ISAT'.

A log rank test stratified by same stratification factors used in the MFS analysis will be used to compare the darolutamide treated and placebo groups.

The hazard ratio as well as its 95% CI will be generated with a Cox regression model as for MFS.

Kaplan-Meier survival curves (product-limit estimates) will be presented by treatment arm. The Kaplan-Meier estimate of the median time to initiation of subsequent antineoplastic therapy and first and third quartiles will be presented with 95% CIs.

A summary of first subsequent antineoplastic therapy will be provided.

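### Time to subsequent antineoplastic therapy carries two incompatible event rules: a window opening 19–22 weeks after the last dose, and any therapy recorded on study

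*Protocol*

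**What the plan says.** The definition in Protocol 6.3.3.3 is clear: "Time to initiation of subsequent antineoplastic therapy is defined as time from randomisation to initiation of first antineoplastic therapy". The next sentence narrows it: "Subsequent antineoplastic therapy will be assessed from the first follow-up visit until the first use of such therapy". SAP 6.2.3.3 repeats both.

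SAP Table 16 states the event differently, as "Recorded antineoplastic therapy during the study", with no earliest date. It sets the event date at the first assessment that qualified. SAP Appendix 9.8 selects the drugs by ATC code from the concomitant-medication (CM) dataset.

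Three timing rules bear on this:

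- Next therapy (Protocol 4.7.1, 5.7.2 and 6.1.2.6): "Another systemic antineoplastic therapy may be initiated no sooner than 7 days after the last dose of study treatment".
- End-of-study treatment visit (Protocol 6.1.2.6): "Patients will have an end-of-study treatment visit 28 days (+7 days) after the last dose of study treatment".
- Follow-up visits (Protocol Table 4): "Every 16 weeks (±7 days) from end-of-study treatment visit".

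For patients who start a prohibited drug before metastasis, the note after Protocol Table 4 says: "Patients initiating a prohibited treatment before confirmed metastasis will be followed only for survival status every 16 weeks until the end of the study". Protocol 4.7.2 instead sends patients who withdraw before metastasis to the Table 4 schedule whether or not they receive prohibited antineoplastic therapy.

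**The concern.** A window that opens at the first follow-up visit does not fit an endpoint that counts from randomisation to the first new therapy. The comparable endpoints are written without it: Protocol 6.3.2.3 (cytotoxic chemotherapy) and 6.3.3.2 (invasive procedures) both assess from randomisation.

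The SAP section therefore holds two rules, and a programmer has to choose. Under the window rule the earliest switchers can leave the event count. Under Table 16 they stay in, but may be dated by a visit instead of by the start of the drug. Two analysts following the same text could report different event counts and different medians.

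**Working it through.** The plan gives no figure for this endpoint to reproduce. The check is visit-window arithmetic followed by a comparison of the rules.

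**1. When the window opens.** Days after the last dose = end-of-study treatment visit (28 to 35) + 16 weeks ±7 days (105 to 119).

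- Earliest: 28 + 105 = 133 days = 19.0 weeks.
- Latest: 35 + 119 = 154 days = 22.0 weeks.
- Nominal: 28 + 112 = 140 days = 20.0 weeks.
- From the earliest permitted start (day 7): 133 − 7 = 126 to 154 − 7 = 147 days, or 18 to 21 weeks.

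**2. Whether data go uncollected in that span.**

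- Day 7 to day 28–35: Protocol 5.7.1 requires all concomitant treatments on the CRF from consent to the end-of-study treatment visit.
- Day 28–35 to day 133–154: Protocol 5.7.1 and Table 3 footnote 11 require antineoplastic therapy to be recorded after withdrawal from study treatment. The CRF question cited under SAP Table 11, "Has the patient taken any new antineoplastic therapy since previous visit", looks back from the first follow-up visit to the end-of-study treatment visit.
- Uncovered days under these rules: 0.

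**3. What each rule does with the same patient.**

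| Therapy start | Window sentence applied as a limit | SAP Table 16 |
|---|---|---|
| Day 7 to the end-of-study treatment visit | Excluded: it precedes the window, and the look-back question is truthfully answered no | Event |
| Between that visit and the first follow-up visit | Event through the look-back; excluded if the limit is put on the start date itself | Event |
| Prohibited antineoplastic drug that ended study treatment | Excluded: it precedes the window, and under survival-only follow-up no such visit is scheduled | Event |
| GnRH therapy continued from before randomisation | Not an event | Not explicitly excluded |

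The last row shows why deleting the sentence is not enough. SAP 6.2.3.3 and Appendix 9.8 select all of ATC class L02 and do not exempt GnRH agents. Appendix 9.6 does exempt L02AE when it lists prohibited drugs for metastasis-free survival (MFS). Patients without orchiectomy must stay on GnRH therapy (Protocol 4.2 and 5.7.1).

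**4. How far a literal event date could move.** Delay = assessment day − start day, converted with the SAP's 30.44 days per month.

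- Day-7 start dated at the end-of-study treatment visit: 28 − 7 = 21 to 35 − 7 = 28 days (0.7 to 0.9 months).
- Day-7 start dated at the first follow-up visit: 126 to 147 days (4.1 to 4.8 months).
- Start just after the end-of-study treatment visit, dated at the first follow-up visit: up to 105 to 119 days (3.4 to 3.9 months).

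**The case against.** The strongest reply is that nothing is lost. Every start from day 7 must be recorded, the endpoint is drawn from the CM dataset, and Table 16 has no earliest date. In Table 16 the CRF question serves only to set censoring dates, so a negative answer at the first follow-up visit does not erase a recorded drug. On this view the sentence merely says when a dedicated question is first scheduled.

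Most of that stands. A reader might infer that the earliest switchers are missed or are dated by a later drug. The documents do not support this: it would happen only if the sentence were used as a filter, against Table 16 and Appendix 9.8.

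A reader might also infer that everyone who starts a prohibited drug before metastasis is lost to this endpoint. That does not follow either. Protocol 4.7.1 still invites these patients to the end-of-study treatment visit, concomitant treatments are recorded up to it, and SAP Appendix 9.6 already takes prohibited drugs from the same CM dataset to censor MFS. Survival-only follow-up is itself contradicted by Protocol 4.7.2.

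What the reply does not answer is that the window is written into the endpoint text of both documents and is the only explicit lower limit there. The words subsequent and initiation do imply new therapy, and a supplementary document that is not available here holds the sponsor's drug assessment. Neither tells the reader of the SAP which rule governs, nor which date to use.

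**Conclusion.** The point holds as an internal contradiction in the operative endpoint text, not as a demonstrated loss of data. The window opens 19–22 weeks after the last dose, against a permitted start at day 7. If it is applied as a limit, it removes starts before the end-of-study treatment visit and prohibited therapies that ended study treatment. If Table 16 is read literally, an early start moves by 21–28 days, or by up to 126–147 days when it is dated at the first follow-up visit. These are consequences of possible readings; the documents do not show which reading was programmed.

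Two further inferences should be left out. An assumed median time to next therapy would give the share of starts exposed to the rule, not the number lost. A direction of bias between arms is also unproven: the documents give no timing of next therapy by arm.

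The weight is limited. The endpoint lies outside the hierarchical testing in SAP 6.2.2, and SAP 6.2.3 gives its p-value informative status only. No confirmatory conclusion depends on it. It should still be corrected, because the text as written does not define one event.

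**What to change.** 1. In Protocol 6.3.3.3 and SAP 6.2.3.3, replace the window sentence by: *assessed from randomisation; the event date is the recorded start date of the first new systemic antineoplastic therapy initiated after randomisation, wherever recorded (concomitant treatments or follow-up).*
2. State in the SAP that background GnRH therapy continued from before randomisation does not count as an event.
3. In SAP Table 16, use the therapy start date as the event date in place of the date of the first qualifying assessment.
4. Reconcile Protocol 4.7.2 with Sections 3 and 4.7.1 and the note after Table 4 on follow-up once a prohibited therapy has started. The passages conflict, and the choice between them is for the sponsor.

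The cost is wording in both documents: a SAP update and a protocol text correction. The start dates should already be in the CM dataset under the existing recording rules, so no new data collection is needed for this endpoint.
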